#### 3.2 Secondary Objectives

- To assess efficacy by response (CR, CRp, CRI, and CR + CRp + CRI) rate and duration and Event Free Survival (EFS)
- To assess safety by 30-day mortality, serious adverse events (SAE) and adverse event frequency and severity
- To assess QOL using FACT-LEU
- To assess the relationship of cognitive function to outcome using the Blessed Orientation-Memory-Concentration Test and the Montreal Cognitive Assessment
- To confirm the safety and practicality of CPX-351 as consolidation therapy
- To supplement efficacy assessment by determining the rate of morphologic leukemia-free state (MLFS)

### 4 Study Design

This is an open label study to assess the suitability of CPX-351 as first intensive therapy in elderly (age  $\geq 60$  years) patients with AML. Patients may have received prior AML treatment with non-intensive regimens, e.g. hypomethylating agents, low dose Ara C or lenolidomide, but may not have received intensive AML treatment with anthracyclines and/or cytarabine prior to enrollment on this trial. The outcome of elderly patients following intensive treatment with CPX-351 will be measured by clinical endpoints for efficacy and safety and by biological/functional response.

#### 4.1 Patient Recruitment

All patients will be screened for study suitability by a principal investigator or sub-investigator prior to entry on the study. An explanation of the study and discussion of the expected risks and benefits will be fully discussed with patients prior to the screening process in order for the patient to provide a voluntary written informed consent. Only eligible and consenting patients will be entered into the study.

## 4.2 Patient Sample Size

Early mortality (30 day mortality) in newly diagnosed fit older (age  $\geq 60$  years) patients with AML initially treated with standard induction therapy with daunorubicin and cytarabine is approximately 20%. Older patients with AML who are less fit, particularly those initially treated with non-intensive regimens, are expected to have 60-day mortality of approximately 40%. After 15 patients have been treated and followed for 30 days or more, early mortality will be assessed. If 30-day mortality exceeds 20% ( $>3$  of the initial 15 patients), *all further accrual will stop*. Subsequent enrollment after the first 15 subjects should ideally resume after the safety analysis is complete, however recognizing the acute nature of AML, it might not be possible to deny treatment to subjects in screening for ethical reasons sufficiently long to evaluate safety or efficacy. In other words, if the 30-day mortality for the preceding patients is less than 20%, study accrual will continue during the DSMB's safety analysis.

In the event that more than 15 subjects have enrolled before the safety analysis, only the first 15 subjects dosed will be informative for determining need for dose reduction.

Study enrollment will be completed within approximately 2 years.

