### 3 Study Objectives and Rationale

#### 3.1 Primary Objectives

- To assess the feasibility of CPX-351 as first intensive therapy in elderly (age  $\geq 60$  years) patients with AML based on safety and efficacy and to evaluate cognitive function in these patients and its relationship to outcome. CPX-351 alone will be declared feasible if one or two induction courses (3 doses or 5 doses) can be delivered to patients with acceptable 30-day mortality. The primary efficacy endpoint will be overall survival (OS). The primary safety endpoint will be early mortality defined as 30-day mortality.

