## 7.3 Dose Reductions and Delays

It is the intention of the study to treat every patient at full dose. Dose delays or modifications will be recommended at the discretion of the treating physician and PI. Doses may be delayed due to toxicities (for example hypersensitivity reactions). Any doses missed or delayed due to toxicity may be administered as soon as the patient has recovered from the toxicity. Toxicities will be graded using the CTCAE Version 4.0. See APPENDIX 4: Common Terminology Criteria for Adverse Events V4.0 (CTCAE)). Toxicities for cytarabine and daunorubicin are relatively well known, and are outlined in the product information for each of these drugs. Furthermore, dose reductions or protocol closure will be considered:

- 1) If >2 of the first 5 patients or >3 of the first 15 patients experience grade 4 toxicities, accrual will stop, the protocol reviewed, and dose modifications considered. If the incidence of grade 4 toxicity exceeds 20% of patients at any point after the first 15 patients have been treated, accrual will stop, the protocol will be reviewed, and dose modifications considered.
  
- 2) If 30-day mortality exceeds 20% (>3 of the initial 15 patients), *all further accrual will stop*. Subsequent enrollment after the first 15 subjects should ideally resume after the safety analysis is complete, however recognizing the acute nature of AML, it might not be possible to deny treatment to subjects in screening for ethical reasons sufficiently long to evaluate safety or efficacy. In other words, if the 30-day mortality for the preceding patients is less than 20%, study accrual will continue during the DSMB's safety analysis.

In the event that more than 15 subjects have enrolled before the safety analysis, only the first 15 subjects dosed will be informative for determining need for dose reduction as outlined in section 4.2.

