## **11 Statistical Considerations**

The primary objective of this non-randomized open label study is to evaluate the safety and efficacy of CPX-351 as a treatment for AML in elderly ( $\geq 60$  years of age) patients. Dose reductions or protocol closure will be considered:

- 1) If  $>2$  of the first 5 patients or  $>3$  of the first 15 patients experience grade 4 toxicities, accrual will stop, the protocol reviewed, and dose modifications considered. If the incidence of grade 4 toxicity exceeds 20% of patients at any point after the first 15 patients have been treated, accrual will stop, the protocol will be reviewed, and dose modifications considered.
- 2) If 30-day mortality exceeds 20% ( $>3$  of the initial 15 patients), *all further accrual will stop*. Subsequent enrollment after the first 15 subjects should ideally resume after the safety analysis is complete, however recognizing the acute nature of AML,

it might not be possible to deny treatment to subjects in screening for ethical reasons sufficiently long to evaluate safety or efficacy. In other words, if the 30-day mortality for the preceding patients is less than 20%, study accrual will continue during the DSMB's safety analysis.

In the event that more than 15 subjects have enrolled before the safety analysis, only the first 15 subjects dosed will be informative for determining need for dose reduction as outlined above.

Patients who die within the first 7 days because of leukemia related toxicity will be replaced. Those patients will be included in the analysis given the intention to treat for 30 day mortality and overall survival.

Analyses will primarily be descriptive in nature. Categorical variables will be summarized as frequency counts with associated percentages and continuous variables will be summarized as mean, standard deviation, median and range. Exact confidence intervals will be computed using the Clopper-Pearson method.

All analyses will be performed using SAS version 9.2 or higher.

Additional details regarding statistical analyses may be presented in a Statistical Analysis Plan (SAP).

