## **11.1 Primary and Secondary Endpoints**

### *11.1.1 Primary Endpoints*

In the CPX-351 cohort, the primary efficacy endpoint is overall survival (OS) as defined in Section 8.2; the primary safety endpoint is the 30-day mortality rate.

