## **11.7 Data Safety Monitoring Board (DSMB)**

Weill Cornell Medical College requires that all research approved by the WCMC IRB include an appropriate plan for the monitoring of data to ensure the safety of human subjects. Research supported by Federal agencies will be monitored according to all regulations and guidelines of the relevant Federal agency.

The WCMC Data and Safety Monitoring Board (DSMB) will review the IRB approved protocol, informed consent documents, and data and safety monitoring plan prior to study initiation. During the course of the study, the DSMB will perform safety analysis as outlined in 4.2 after 15 subjects have enrolled.

After the initial safety analysis period, the DSMB will review the cumulative study data semiannually to evaluate safety, efficacy, study conduct, and scientific validity and integrity of the trial. In particular, the results of the Day 30 echocardiogram will be included in the DSMB Periodic Reports. The WCMC DSMB may also convene as needed if stopping criteria are met or other safety issues arise that the Principal Investigator and/or IRB would like the WCMC DSMB to address. The study PI will submit all written DSMB recommendations to the IRB upon receipt.

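### The 20% limit on 30-day mortality is applied once, at 15 patients; no numeric mortality trigger covers patients 16 to 30

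*Combined protocol and SAP*

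**What the plan says.** Section 11.1.1 states that "the primary safety endpoint is the 30-day mortality rate", and Section 3.1 calls the regimen feasible if induction "can be delivered to patients with acceptable 30-day mortality", without giving a figure.

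Section 4.2 sets the timing of the mortality check: "After 15 patients have been treated and followed for 30 days or more, early mortality will be assessed". Section 7.3 gives its limit: "If 30-day mortality exceeds 20% (>3 of the initial 15 patients"), in which case all accrual ends. Sections 4.2 and 11 carry the same rule. All three sections add that, if more than 15 have enrolled by then, only the first 15 dosed inform the decision on dose reduction.

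The item directly above it in the lists of Sections 7.3 and 11 behaves differently. It has early limits too, but then continues: "If the incidence of grade 4 toxicity exceeds 20% of patients at any point after the first 15 patients have been treated", accrual stops and the protocol is reviewed.

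After the first safety analysis, Section 11.7 says "the DSMB will review the cumulative study data semiannually". The board may also meet "if stopping criteria are met or other safety issues arise that the Principal Investigator and/or IRB would like the WCMC DSMB to address". Section 11 replaces patients who die in the first 7 days from leukemia-related toxicity, but adds: "Those patients will be included in the analysis given the intention to treat for 30 day mortality and overall survival".

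**The concern.** The plan keeps a running numeric limit for grade 4 toxicity but not for death by day 30, the endpoint on which its feasibility claim rests. A trial with 3 deaths among the first 15 passes. If it then reaches 5 of 20, it stands at 25%, above the plan's own limit, and no written mortality rule requires anyone to pause. Section 11.7 lets the board convene when stopping criteria are met, but after patient 15 no mortality criterion is left to meet. At stake is a prompt, pre-agreed response to deaths in the second half of the cohort, in a population that Section 2.4 expects to be less resilient than the fit older patients of the phase 2 study.

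**Working it through.** **Inputs.** The limit is more than 3 deaths in the first 15 (Sections 4.2, 7.3, 11). The total is 30 patients over about 24 months (synopsis; Section 11.2). Reference 30-day mortality rates are 5.9% for CPX-351 and 10.6% for 7+3 in phase 3 (Section 2.4), and about 20% for standard induction in fit older patients (Section 4.2). The other true rates, including 30%, are assumptions. All patients dosed are counted, the total dosed is taken as 30, and outcomes are independent binomial.

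**The plan's own figure.** 3/15 = 20.0% does not exceed 20%; 4/15 = 26.7% does. So more than 3 of 15 matches the stated 20%. The plan gives no operating characteristics for the rule.

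**Step 1: the single look at a true 30%.** With X deaths in the first 15 and Y in the next 15, P(pass) = P(X ≤ 3) = 0.0047 + 0.0305 + 0.0916 + 0.1700 = 0.297 (29.7%).

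**Step 2: pass, then finish above 20%.** Above 20% of 30 means at least 7 deaths, so sum P(X = x) × P(Y ≥ 7 − x) over x = 0 to 3:

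- x = 0: 0.0047 × 0.1311 = 0.0006
- x = 1: 0.0305 × 0.2784 = 0.0085
- x = 2: 0.0916 × 0.4845 = 0.0444
- x = 3: 0.1700 × 0.7031 = 0.1196

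The total is 0.1730 (17.3% of all trials at this rate; 0.1730/0.2969 = 58% of those that pass).

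**Step 3: sensitivity at exactly 3 of 15.** Most of the 17.3% comes from x = 3. If 3/15 also halted accrual, that term drops out. P(pass) becomes 0.0047 + 0.0305 + 0.0916 = 12.7%, and pass-and-finish-above-20% becomes 0.00062 + 0.00850 + 0.04436 = 0.05348 (5.3%).

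**Step 4: add looks at 20 and 25.** 4/20 = 5/25 = 20%, so the first counts above the limit are 5 of 20 and 6 of 25. At a true 30% the probabilities of first crossing at 15, 20 and 25 are 0.7031, 0.0961 and 0.0567, which sum to 0.856. The added looks contribute 0.0961 + 0.0567 = 15.3 points (3.9 points if 3/15 already halts).

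| True 30-day mortality | Stop, single look | Stop or pause, three looks | Passes the single look, ends above 20% | Passes all three looks, ends above 20% |
|---|---|---|---|---|
| 5.9% | 1.0% | 1.2% | | |
| 10.6% | 6.6% | 9.1% | | |
| 15% | 17.7% | 25.0% | | |
| 20% | 35.2% | 48.6% | 13.5% | 4.0% |
| 25% | 53.9% | 70.4% | 18.1% | 4.7% |
| 30% | 70.3% | 85.6% | 17.3% | 3.7% |
| 40% | 91.0% | 98.0% | 7.8% | 1.0% |

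**Step 5: patients spared at a true 30%.** If every pause became a closure, 10 × 0.0961 + 5 × 0.0567 = 1.2 fewer patients would be dosed. If 1.25 patients (30/24 per month) enrol while day-30 status matures at each look, this is 8.75 × 0.0961 + 3.75 × 0.0567 = 1.05.

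**Step 6: the alternative of copying the grade 4 wording.** A limit of more than 20% checked after every patient from 15 to 29 would trigger in 94.0% of trials at a true 30%, but also in 16.6% at 10.6% and 65.4% at 20%.

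**The case against.** The strongest reply is that oversight does not end at patient 15. At 1.25 patients a month, patients 16 to 30 take about 15/1.25 = 12 months, so about two semiannual DSMB reviews fall in that period, roughly one per 7 or 8 patients. Every death is an SAE, reported within 24 hours, and SAE reports are compiled for the board (Sections 9.2.2 to 9.2.4). The grade 4 limit continues and does not exclude hematologic toxicity; since Section 2.4 links most grade 3/4 events to myelosuppression, it may stop accrual first. All of this stands. A reader might infer that mortality goes unmonitored after patient 15, or that 29.7% and 17.3% describe the whole trial. The documents support neither: the figures ignore the grade 4 limit and DSMB discretion. But none of these safeguards states a 30-day mortality threshold.

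Second, 30% is not a rate from the documents. The 40% in Section 4.2 is 60-day mortality in less fit patients. At the phase 3 rate of 5.9% the added looks change almost nothing, and at 40% the existing look already stops 91.0%. The gain is concentrated around 25% to 30%. This also stands.

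Third, Sections 4.2, 7.3 and 11 let accrual continue during the DSMB's analysis only when mortality so far is below 20%, which 3/15 is not. That sentence governs only the period of that analysis and is not a limit for patients 16 to 30, and the explicit cut-off of more than 3 supports treating 3/15 as a pass. The size of the problem does depend on it, as Step 3 shows.

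Finally, a single early look with standing review is a defensible choice for a 30-patient, mainly descriptive study. Nothing here shows that the cut-off of more than 3 of 15 is wrong.

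**Conclusion.** The point holds as a gap in the written rule: the 20% limit on the primary safety endpoint is tested once, and half the planned cohort follows with no numeric mortality trigger. By the mortality rule alone, at an assumed true 30%, 29.7% of trials pass and 17.3% pass and finish above 20%. These rest on 3/15 counting as a pass; otherwise they are 12.7% and 5.3%.

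Two benefits of the added looks are easy to overread. The fall from 17.3% to 3.7% counts trials that end above 20% with no written mortality trigger having fired. It is not the fall in trials that end above 20%, because a paused trial may resume and still do so. The saving of about 1.2 patients is an upper bound that holds only if every pause becomes a closure. The real gain is a pre-agreed mortality review when deaths pass the plan's own limit. Severity: minor to moderate.

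**What to change.** Keep more than 3 of 15 as it is, and add one sentence to Sections 4.2, 7.3 and 11:

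*Accrual also pauses, pending DSMB review, if 5 or more of the first 20, or 6 or more of the first 25, patients dosed have died by day 30; patients replaced after an early death are counted.*

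Counting replaced patients follows what Section 11 already does for 30-day mortality. Print the stop-or-pause probabilities beside the rule so that the DSMB knows how it behaves. Two looks are preferable to an at-any-time limit because of the false alarms in Step 6.

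The cost is amendment wording and two extra death counts, with no added patients or procedures. The downside is more pauses at rates the sponsor may accept: 6.6% to 9.1% at a true 10.6% and, chiefly, 35.2% to 48.6% at a true 20%. For that reason the new looks pause accrual for review and do not close the trial. Patients 26 to 30 would still have no numeric limit, about 5/1.25 = 4 months of accrual.

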## 4.3 Induction

Following registration, patients will be monitored closely for response and safety. Depending on the type and extent of response as well as toxicity, the patient may continue on to consolidation therapy, receive a second induction, or be discontinued from the Treatment Phase and monitored in the Follow-up Phase.

Dosing for first induction: CPX-351 alone

- CPX-351 at 100u/m^2 will be administered on study days 1, 3 and 5

## 4.4 Repeat of Induction

Patients achieving aplasia/hypoplasia (<5% blast count) will not receive second inductions. Patients with reduced tumor burden and evidence of persistent leukemia who remain fit for additional intensive chemotherapy can be given second inductions up to 60 days (measured from day 1 of chemotherapy treatment) after the first induction treatment date.

Patients unable to achieve a response (CR, CRp, or CRi) after up to 2 inductions are discontinued from further treatment and followed for survival.

Dosing for second induction:

- CPX-351 at 100 u/m^2 will be administered on days 1 and 3

## 4.5 Consolidation Therapy

Only patients with confirmed response (CR or CRp or CRi) and who remain fit for additional chemotherapy are eligible for chemotherapy consolidation. Investigators may

use post remission therapy of their choice or they may choose to use CPX-351. Before consolidation treatment can begin, patients need a repeat echocardiogram and labs to evaluate renal and liver function and must fulfill eligibility criteria initiation of treatment. For patients given CPX-351 post remission therapy: prior to starting consolidation, LVEF must be documented to be  $\geq 50\%$  and patients must have recovered to ANC  $> 500/\mu\text{L}$  and platelets  $> 50,000/\mu\text{L}$  within 56 days after last dose of CPX-351. A second consolidation cycle is permitted provided the first consolidation course was well tolerated and repeat echocardiogram shows an LVEF  $> 50\%$  and ANC and platelets have recovered within 56 days of the start of the last consolidation cycle. Up to 2 consolidation courses are permitted. Scheduling and dose of consolidation treatment may be adjusted depending on degree and rate of patient recovery.

Dosing for consolidation:

- CPX-351 at 65  $\text{u}/\text{m}^2$  will be administered on days 1 and 3

#### 4.6 Follow-up Phase

Patients will be followed at monthly intervals or more frequently depending on clinical circumstances until start of the next salvage treatment, death or for 1 year from date of enrollment. Patients alive and in remission after 1 year will be followed annually or more frequently depending on clinical circumstances for up to 5 years from enrollment. For EFS evaluation, events include: documentation of persistent AML after induction, relapse after achievement of CR/CRp/ CRi, or death. Bone marrow assessments will be performed at any time during follow up when recurrent cytopenias raise the suspicion of AML relapse. After documentation of persistent leukemia or relapse, follow-up for OS will continue. At the start of HSCT or non-protocol AML treatment of any sort or 30-days following the last dose, whichever occurs first, AE data collection will stop.

#### 4.7 Study Modification/Discontinuation

Any modifications to the study will be documented in a revised protocol with a new assigned version. The revised protocol will have an appendix which will detail the revisions to the document.

### 5 Selection and Withdrawal of Patients

#### 5.1 Study Population

##### 5.1.1 *Inclusion criteria*

- 5.1.1.1 Ability to understand and voluntarily give informed consent
- 5.1.1.2 Age  $\geq 60$  years at the time of study treatment
- 5.1.1.3 Pathological diagnosis of AML according to WHO criteria (with  $> 20\%$  blasts in the peripheral blood or bone marrow) including:
- 5.1.1.4 De novo AML with normal karyotype or adverse karyotypes (including patients with karyotypic abnormalities characteristic of MDS)
- 5.1.1.5 Secondary AML: transformed from prior MDS or MPN, confirmed by bone marrow documentation of prior antecedent hematologic disorder

- 5.1.1.6 Therapy-related AML: t-AML, requires documented history of prior cytotoxic therapy or ionizing radiotherapy for an unrelated disease
- 5.1.1.7 Performance status >50% KPS, ECOG 0-2
- 5.1.1.8 Laboratory values fulfilling the following:
  - 5.1.1.9 Serum creatinine < 2.5 mg/dL
  - 5.1.1.10 Serum total bilirubin < 2.5 mg/dL,
  - 5.1.1.11 Serum alanine aminotransferase or aspartate aminotransferase < 3 times the ULN
  - 5.1.1.12 Patients with elevated liver enzymes and serum creatinine values secondary to AML are eligible after discussion with PI
  - 5.1.1.13 Cardiac ejection fraction  $\geq$  50% by echocardiography, MUGA, or Cardiac MRI
  - 5.1.1.14 Patients with history of second malignancies in remission may be eligible if there is clinical evidence of disease stability off cytotoxic chemotherapy, documented by imaging, tumor marker studies, etc., at screening. Patients maintained on long-term non-chemotherapy treatment, e.g., hormonal therapy, are eligible.

#### *5.1.2 Exclusion Criteria*

- 5.1.2.1 Acute promyelocytic leukemia [t(15;17)]
- 5.1.2.2 Clinical or morphologic evidence of active CNS leukemia
- 5.1.2.3 Prior intensive chemotherapy for AML with anthracycline/cytarabine-based regimens and/ or prior HSCT. Patients may have been treated with commercially available or investigational hypomethylating agents (e.g. decitabine, azacitidine, SGI-110), lenalidomide, or low-dose cytarabine (not to exceed 20 mg/m^2 daily for 14 days for  $\leq$  6 cycles)
- 5.1.2.4 Prior treatment including HMA, systemic chemotherapy, surgery, or radiation therapy must have been completed at least 7 days before start of study treatment or after discussion with PI. Treatment with investigational agents must have been completed at least 14 days prior to study drug treatment. Hydroxyurea is permitted for control of blood counts before the start of study treatment. Toxicities associated with prior therapies must have recovered to grade 1 or less prior to start of study treatment.
- 5.1.2.5 Patients with prior cumulative anthracycline exposure of greater than 368 mg/m^2 daunorubicin (or equivalent).
- 5.1.2.6 Any serious medical condition, laboratory abnormality or psychiatric illness that would prevent obtaining informed consent
- 5.1.2.7 Patients with myocardial impairment of any cause (e.g. cardiomyopathy, ischemic heart disease, significant valvular dysfunction, hypertensive heart disease, and congestive heart failure) resulting in heart failure by New York Heart Association Criteria (Class III or IV staging)
- 5.1.2.8 Active or uncontrolled infection. Patients with an infection receiving treatment (antibiotic, antifungal or antiviral treatment) may be entered into the study but must be afebrile and hemodynamically stable for  $\geq$ 72 hrs.

- 5.1.2.9 Patients with current or recent evidence of invasive fungal infection (blood or tissue culture); patients with recent fungal infection must have a subsequent negative cultures to be eligible
- 5.1.2.10 Known HIV (new testing not required) or evidence of active hepatitis B or C infection (with rising transaminase values)
- 5.1.2.11 Hypersensitivity to cytarabine, daunorubicin or liposomal products
- 5.1.2.12 History of Wilson's disease or other copper-metabolism disorder
- 5.1.2.13 History of prior bone marrow or solid organ transplantation

